5.3.1. Meals and Dietary Restrictions

Per the Schedule of Activities (Section 1.3), study participants will receive diet counselling by a dietician/nutritionist, or equivalent qualified delegate, according to JASSO guidelines. Dietary counseling will consist of advice on healthy food choices and focus on calorie restriction using a hypocaloric diet with macronutrient composition of

- Approximately 50% to 60% of energy from carbohydrate
- Approximately 15% to 20% of energy from protein
- Approximately 20% to 25% of energy from fat, and
- Daily energy intake up to 25 kCal/kg × standard body weight (as determined by BMI = 22 kg/m²) for the participant whose BMI is ≥ 27 kg/m² and 20 to 25 kcal/kg × standard body weight for the participant whose BMI is ≥ 35 kg/m².

To encourage adherence, it is recommended that a 3-day diet and exercise diary be completed prior to each counseling visit. During each visit, the participant's diet is reviewed and advice to maximize adherence is provided if needed.

The recommended diet is continued after randomization and throughout the treatment period. Dietary evaluation and appetite sensation are described in Sections 8.1.2.9.5.1 and 8.1.2.9.5.2, respectively.

5.3.2. Caffeine, Alcohol, and Tobacco for PK/PD Visits

- 1. During each dosing session at the site visit, participants will abstain from ingesting caffeine- or xanthine-containing products (e.g., coffee, tea, cola drinks, and chocolate) for at least 10 hours before the start of dosing until after collection of the final PK and/or PD sample.
- 2. During each dosing session at the site visit, participants will abstain from alcohol for 24 hours before the start of dosing until after collection of the final PK and/or PD sample.
- 3. Participants who use tobacco products will be instructed that use of nicotine-containing products (including nicotine patches) will not be permitted while they are in the clinical unit. Use of tobacco products will be abstained for 8 hours before the start of dosing until after collection of the final laboratory sampling.

5.3.3. Physical Activity

Participants will abstain from strenuous exercise for 24 hours before each blood collection for clinical laboratory tests. Participants may participate in light recreational activities during onsite study procedures (e.g., watching television, reading).

At Visit 3 and all subsequent visits, participants will be advised to increase their physical activity to at least 150 minutes per week. Please see Appendix 13 (Section 10.13) for detail guidance of physical activity.

5.4. Screen Failures

Screen failures are defined as participants who consent to participate in the clinical study but are not subsequently randomly assigned to the study intervention. A minimal set of screen failure information is required to ensure transparent reporting of screen failure participants to meet the Consolidated Standards of Reporting Trials (CONSORT) publishing requirements and to respond to queries from regulatory authorities. Minimal information includes demography, screen failure details, eligibility criteria, and any serious adverse events (SAEs).

Individuals who do not meet the criteria for participation in this study (screen failure), will have an opportunity to have 1 additional screening visit with repeat screening laboratory tests at the discretion of the investigator. Before rescreening is performed, the patient must sign a new ICF and receive a new identification number. If, in the opinion of the investigator, an ineligible laboratory test result is the result of an error or extenuating circumstance, then that parameter can be retested once without the patient having to be rescreened.

6. Study Intervention

Study intervention is defined as any investigational intervention(s), marketed product(s), placebo, or medical device(s) intended to be administered to/used by a study participant according to the study protocol.

6.1. Study Intervention(s) Administered

ARM Name	Tirzepatide 10 mg	Tirzepatide 15 mg	Placebo
Dosage Level(s)	10 mg QW	15 mg QW	Placebo QW
Route of Administration	SC	SC	SC
Sourcing	Provided centrally by the sponsor and dispensed via IWRS		
Packaging and Labeling	Study Intervention will be provided in autoinjectors (single-dose pens), packaged in cartons to be dispensed. Clinical study materials will be labeled according to country regulatory requirements.		

Abbreviations: IWRS = interactive web response service; QW = once-weekly; SC = subcutaneous.

There are no restrictions on the time of day each weekly dose of study intervention is given, but it is advisable to administer the SC injections on the same day and same time each week. The actual date, time and injection site location of all dose administrations will be recorded in the diary by the participant. If a dose of study intervention is missed, the participant should take it as soon as possible unless it is within 72 hours of the next dose, in which case that dose should be skipped, and the next dose should be taken at the appropriate time. The day of weekly administration can be changed if necessary, as long as the last dose was administered 72 or more hours before.

All participants will inject study intervention subcutaneously in the abdomen or thigh using the injection supplies provided; a caregiver may administer the injection in the participant's upper arm. The injection site location of all dose administrations will be recorded by the participant. A new autoinjector will be used for each injection. If study intervention is to always be injected in the same body region, participants should be advised to rotate injection sites each week.

6.1.1. Medical Devices

The product provided for use in the study is tirzepatide investigational autoinjector (or matching placebo). Any medical-device incidents, including those resulting from malfunctions of the device, must be detected, documented, and reported by the investigator throughout the study (see Section 10.9).

All product complaints (including malfunction, use error and inadequate labelling) shall be documented and reported by the investigator throughout the clinical investigation (see Section 8.3) and appropriately managed by the sponsor.

6.2. Preparation/Handling/Storage/Accountability

- The investigator or designee must confirm appropriate temperature conditions have been maintained during transit for all study intervention received and any discrepancies are reported and resolved before use of the study intervention.
- Only participants enrolled in the study may receive study intervention and only authorized site staff may supply or administer study intervention. All study intervention must be stored in a secure, environmentally controlled, and monitored (manual or automated) area in accordance with the labeled storage conditions with access limited to the investigator and authorized site staff.
- Study site staff must regularly assess whether the participant is correctly administering the assigned study intervention and storing study drug according to the provided instructions
- The investigator, institution, or the head of the medical institution (where applicable) is responsible for study intervention accountability, reconciliation, and record maintenance (i.e., receipt, reconciliation, and final disposition records).
- Further guidance and information for the final disposition of unused study interventions are provided in the study training documents.

6.3. Measures to Minimize Bias: Randomization and Blinding

Interactive web-response system

All participants will be randomly assigned to study intervention using a central interactive-web response system (IWRS) at the end of Visit 3 after participant's eligibility is confirmed. Before the study is initiated, the log in information and directions for the IWRS will be provided to each site. Study intervention will be dispensed at the study visits summarized in the Schedule of Activities (Section 1.3).

The randomization will be stratified by

- baseline IGT (yes or no)
- baseline hyperlipidemia (yes or no)
- baseline NAFLD (yes or no), and
- sex

Blind break

Investigators, site staff, clinical monitors and participants will remain blinded to the treatment assignments until the study is complete.

The IWRS will be programmed with blind-breaking instructions. In case of an emergency, the investigator has the sole responsibility for determining if unblinding a participant's intervention assignment is warranted. Participant safety must always be the first consideration in making such a determination. If a participant's intervention assignment is unblinded, the sponsor must be notified immediately after breaking the blind. The date and reason that the blind was broken must be recorded in the source documentation.

If an investigator, site personnel performing assessments, or participant is unblinded, the participant must be discontinued from the study. In cases where there are ethical reasons to have the participant remain in the study, the investigator must obtain specific approval from a Lilly clinical research physician (CRP) and/or clinical research scientist (CRS) for the participant to continue in the study.

6.4. Study Intervention Compliance

Participant compliance with study intervention will be assessed at each visit. Compliance will be assessed by direct questioning, reviewing the study diary, and counting of unused study drug and/or empty cartons returned.

Treatment compliance for each visit interval is defined as taking at least 75% of the required doses of study drug. Similarly, a participant will be considered significantly noncompliant if he or she is judged by the investigator to have intentionally or repeatedly taken more than the prescribed amount of medication (more than 125%).

Participants considered to be poorly compliant with their medication and/or the study procedures will receive additional training and instruction, as required, and will be reminded of the importance of complying with the protocol.

6.5. Concomitant Therapy

Participants are permitted to use concomitant medications that they require during the study, with the exception of certain medications (for example; other medications for weight management) that may interfere with the assessment of efficacy and safety characteristics of the study treatments.

Any concomitant medications taken for obesity-related health problems on a stable dose for at least a period of 3 months prior to study entry will be permitted. Dosage change during the study will only be allowed if concerns for safety issue are identified.

Participants who develop DM during the study may initiate medication for glucose control, with the exception of dipeptidylpeptidase-4 (DPP-4) inhibitors or GLP-1 receptor agonists. Initiation of metformin for the treatment of DM is permitted, but metformin should not be initiated during the study for the treatment of other metabolic conditions (for example, polycystic ovarian syndrome, diabetes prevention).

Investigative site staff will inform participants that they must consult with the investigator or a designated site staff member upon being prescribed any new medications during the study. This may not be possible when initiated for treatment of medical emergencies, in which case, the participant will inform the investigator or a designated site staff member as soon as possible.

Any medication or vaccine (including over-the-counter or prescription medicines, vitamins, and/or herbal supplements) that the participant is receiving at the time of enrollment or receives during the study must be recorded along with:

• Reason for use

- Dates of administration including start and end dates
- · Dosage information including dose and frequency

The medical monitor should be contacted if there are any questions regarding concomitant or prior therapy.

Non-study medications taken by participants who are screened but not randomized will not be reported to Lilly unless an SAE or AE occurs that the investigator believes may have been caused by a study procedure.

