6.7. Management of Incident Diabetes

Participants who develop diabetes during the study will be

- · provided and trained to use a glucometer
- · educated on the signs and symptoms of hypoglycemia and its treatment, and
- provided a diary to record hypoglycemic episodes per Section 10.4.7.1.

Participants will be referred to their usual care provider and provided with a letter showing the study results indicative of diabetes. The decision to further evaluate, to initiate antihyperglycemic therapy, and the choice of antihyperglycemic medication will be at the discretion of the participant's usual care provider, with the exception of use of DPP-4 inhibitors and GLP-1R agonists, which are prohibited in the study. Monitoring for hypoglycemia includes capture of events as defined in Section 10.4.7.1. Date of diagnosis of diabetes will be captured in the electronic case report form (eCRF).

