#### 1.1.2.1. Primary estimand

The estimand is described by the following attributes:

- Population: all randomized participants who received at least 1 dose of treatment.
- Endpoint: mean percent change from randomization to Week 72 in body weight, AND percentage of study participants who achieve ≥5% body weight reduction from randomization to Week 72.
- Treatment condition of interest: tirzepatide 10 mg and/or 15 mg QW vs. placebo, excluding data after discontinuation of study drug. Temporary interruptions and modification prior to discontinuation will be allowed as part of the treatment conditions.
- Handling of intercurrent events: the intercurrent events of treatment discontinuation for any reason is addressed by the treatment condition of interest attribute and handled by the hypothetical strategy.
- Population-level summary: difference in mean percent changes between treatment conditions, AND difference in response percentage between treatment conditions.

Rationale for estimand: the estimand aims to reflect treatment efficacy in an envisaged scenario in which the intercurrent events leading to treatment discontinuation would not occur.

This estimand is referred to as 'efficacy' estimand in the latter of this document.

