# 3. Analysis Sets

For purposes of analysis, the following populations are defined:

Table GPHZ.3.1. Description of Analysis Populations

Population	Description
Entered	All participants who sign informed consent form (ICF)
Randomized	All participants who are randomly assigned a study drug.
Modified Intent-to-Treat (mITT)	All randomly assigned participants who are exposed to at least 1 dose of study drug. Participants will be included in the treatment group to which they were randomized.

Table GPHZ.3.2. Description of Analysis Datasets

Analysis Datasets	Description
Efficacy Analysis Set (EAS)	Data obtained during the treatment period from the modified intent-to-treat (mITT) population, excluding data after discontinuation of study drug (last dose date + 7 days)
	Regarding imaging measurements (MRI and CT), data obtained during the treatment period from the mITT population, excluding data after discontinuation of study drug (last dose date + 14 days)
Full Analysis Set (FAS)	Data obtained during treatment period from the mITT population, regardless of adherence to study drug.
Safety Analysis Set (SS)	Data obtained during the treatment plus follow up period from the mITT population, regardless of adherence to study drug.

Unless otherwise specified, for analyses guided by the "efficacy" estimand, EAS will be used. For analyses guided by the "treatment-regimen" estimand, FAS will be used. For safety analysis, SS will be used.

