#### 4.4.1.2. Defined Obesity-Related Health Problems

The definition of baseline obesity-related health problems (ORHPs) are:

- IGT from 2-hour OGTT results: Fasting glucose or 0-hour OGTT = 110-125 mg/dL (6.1-6.9 mmol/L) and/or 2-hour OGTT = 140-199 mg/dL (7.8-11.0 mmol/L).
- **Hyperlipidemia**: triglyceride (TG) ≥150 mg/dL at baseline
- NAFLD: HFF  $\geq$ 5% by MRI at baseline

Definition of IGT is based on the GPHZ protocol (b). For each subjects, baseline ORHPs are determined by the measurements (not by the inputs of IWRS).

The definition of improvements of each defined obesity-related health problems are:

- **IGT** (only for participants with IGT at baseline)
  - o Return to normal blood glucose range
    - OGTT 0-hour glucose <110 mg/dL AND

- OGTT 2-hour glucose <140 mg/dL
- **Hyperlipidemia** (only for participants with hyper-triglyceridemia [triglyceride (TG) ≥150 mg/dL] at baseline)
  - o Return to normal range (TG <150 mg/dL) OR
  - o Reduced by 30% from baseline
- NAFLD (only for participants with diagnosis of NAFLD [HFF ≥5%] by MRI at baseline)
  - o Return to normal range (HFF <5%) OR
  - o Reduced by 30% from baseline

Incident diabetes is followed by Japanese Clinical Practice Guideline for Diabetes 2019 (Araki et al. 2020) and defined when any 1 of the following occur after randomization:

- unequivocal hyperglycemia (random glucose ≥200 mg/dL) with signs or symptoms of hyperglycemia (e.g., dry mouth, polyposia, polyuria, body weight loss, or diabetic retinopathy).
- within a 4 week period, the following laboratory evidence of diabetic type criteria including either HbA1c ≥6.5%, or glucose levels (fasting glucose or OGTT 0 hour glucose ≥126 mg/dL and/or OGTT 2 hour glucose ≥200 mg/dL) are observed:
  - o Both glucose level and HbA1c meets diabetic type criteria
  - o Only glucose level meets diabetic type criteria
    - With typical symptoms of DM or definite diabetic retinopathy
    - Without typical symptoms of DM or definite diabetic retinopathy, re-exam within 1 month and:
      - Both glucose level and HbA1c meets diabetic type criteria
      - Only glucose level meets diabetic type criteria
      - Only HbA1c meets diabetic type criteria
  - o Only HbA1c meets diabetic type criteria, re exam within 1 month and
    - Both glucose level and HbA1c meet diabetic type criteria
    - Only glucose level meets diabetic type criteria
- initiation of any medication for the treatment of diabetes

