## 4.4.3. Secondary and Exploratory Endpoints

Table GPHZ.4.2. Secondary and Exploratory Efficacy Measures for Improvement of Obesity-related Health Problems

Analysis variable	Criteria/Measures	Analysis set	Analysis method	Additional Information
Percentage of participants who met the following criteria at 72 weeks from BL	Improvement in at least 2 obesity related health problems for participants with BL BMI >27 and <35 kg/ m², or Improvement in at least 1 obesity related health problem for participants with BL BMI >35 kg/ m²	Efficacy analysis set	Logistic model in Section 4.4.2.2	Definition of endpoint: 4.4.1.3
	Improvement in at least 2 obesity-related health problems	Efficacy analysis set - participants with BL BMI ≥27 and <35 kg/m²	Logistic model in Section 4.4.2.2	Exploratory
	Improvement in at least 1 obesity-related health problem	Efficacy analysis set - participants with BL BMI ≥35 kg/m 	Logistic model in Section 4.4.2.2	Exploratory
Improvement in laboratory tests for obesity-related health problems (72 weeks)	Mean changes in OGTT 2-hr glucose at 72 weeks from BL	Efficacy analysis set - participants with IGT at BL	MMRM model in Section 4.3.2.1	
	Mean changes in fasting glucose at 72 weeks from BL	Efficacy analysis set - participants with IGT at BL	MMRM model in Section 4.3.2.1	
	Mean changes in Fasting lipids (TG) at 72 weeks from BL	Efficacy analysis set - participants with hyperlipidemia at BL	MMRM model in Section 4.3.2.1	
	Mean changes in HFF at 72 weeks from BL	Efficacy analysis set - participants diagnosed as NAFLD by MRI at BL	ANCOVA model in Section 4.4.2.1	
Improvement of IGT (72 weeks)	Proportion of participants who achieved improvements of IGT	Efficacy analysis set - participants with IGT at BL	Logistic model in Section 4.3.2.2	

Analysis variable	Criteria/Measures	Analysis set	Analysis method	Additional Information
Improvement of hyperlipidemia (72 weeks)	Proportion of participants who achieved improvements of hyperlipidemia	Efficacy analysis set - participants with hyperlipidemia at BL	Longitudinal logistic model in Section 4.4.2.3	
Improvement of NAFLD (72 weeks)	Proportion of participants who achieved improvements of NAFLD	Efficacy analysis set - participants diagnosed as NAFLD by MRI at BL	Logistic model in Section 4.3.2.2	Compare TZP 10 mg, 15 mg and pooled TZP doses with placebo

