Abbreviations: ALT = alanine aminotransferase; AST = aspartate aminotransferase; BL = baseline; eGFR = estimated glomerular filtration rate; ELF = enhanced liver fibrosis; FFA = free fatty acid; FIB-4 = Fibrosis-4; GGT = gamma-glutamyl transferase; HbA1c = glycated hemoglobin; HDL-C = high-density lipoprotein cholesterol; HOMA2-%B = homeostasis model assessment estimates steady state beta cell function; HOMA2-%S = homeostasis model assessment estimates steady state insulin sensitivity; hs-CRP = high-sensitivity C-reactive protein; IGT = impaired glucose tolerance; K-18 (M30) = keratin-18 M30 fragment; LDL-C = low-density lipoprotein cholesterol; MMRM = mixed model for repeated measures; NAFLD = non-alcoholic fatty liver disease; Pro-C3 = a fragment of the NH2-terminal propeptide of type III procollagen; T2DM = type 2 diabetes mellitus; TC = total cholesterol; TG = triglycerides; TNFα = tumor necrosis factor alpha; TZP = tirzepatide; UACR = urine albumin-to-creatinine ratio; VLDL = very low-density lipoproteins.

Unless otherwise stated, the assessment of secondary efficacy objective will be guided by the "efficacy" estimand, using the same population as for primary analysis.

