# Other hypoglycemia categories:

• **Nocturnal hypoglycemia** is defined as any hypoglycemic event that occurs between bedtime and waking.

To avoid duplicate reporting, all consecutive hypoglycemic events occurring within a 1-hour period will be considered as a single hypoglycemic event.

Statistical summaries and analyses will exclude hypoglycemic events occurring after initiation of rescue antihyperglycemic medication. Both the incidence (percent of participants experiencing ≥1 episode) and the rate (episodes/patient/year) of level 2 or level 3 hypoglycemia, and level 3 hypoglycemia will be reported by treatment.

The incidence of hypoglycemic events will be analyzed using logistic regression with treatment and stratification factors as fixed effects. The rate of hypoglycemic episodes per patient year may be analyzed using a generalized linear mixed-effects model assuming the number of hypoglycemic episodes follows a negative binomial distribution with the mean modeled using stratification factors and treatment as fixed effects. A listing of hypoglycemic events will be provided.

If a hypoglycemic event meets the criteria of severe, the event would specifically be collected as an SAE. Serious hypoglycemia is defined by pharmacovigilance criteria and will also be captured with a SAE form.

[figure not shown]
Severe/serious hypoglycemia will be considered as AESIs. The summaries of severe/serious hypoglycemia will be provided by treatment group, if deemed necessary.

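### The IGT and glycemic analyses ignore glucose-lowering drugs started after incident diabetes, so a participant normalised by another drug counts as an IGT improver

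*Protocol*

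**What the plan says.** **Medication.** Protocol 6.5: "Participants who develop DM during the study may initiate medication for glucose control", with DPP-4 inhibitors and GLP-1 receptor agonists excepted. Protocol 6.7 adds that "the choice of antihyperglycemic medication will be at the discretion of the participant's usual care provider". Among glucose-lowering drugs, Protocol 7.1 names only those two classes as a possible reason for permanently stopping study drug, and then only if the participant will not or cannot stop them. A permitted drug can run alongside study drug.

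**Estimand and data set.** In SAP 1.1.2.1, "the intercurrent events of treatment discontinuation for any reason is addressed by the treatment condition of interest attribute" and handled by a hypothetical strategy. No other intercurrent event is named. The EAS (SAP 3) removes only data collected after study drug stops, with a 7-day margin (14 days for imaging). SAP 4.4.3 carries this over: "Unless otherwise stated, the assessment of secondary efficacy objective will be guided by the" efficacy estimand.

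**Endpoints.** SAP 4.4.1.2 defines IGT improvement as "Return to normal blood glucose range", meaning OGTT 0-hour glucose below 110 mg/dL and 2-hour glucose below 140 mg/dL. Neither medication nor intervening diabetes is mentioned. Table GPHZ.4.2 analyses "Proportion of participants who achieved improvements of IGT" on the EAS by logistic regression, and OGTT 2-hour and fasting glucose by MMRM. Table GPHZ.4.4 does the same for fasting glucose, HbA1c, insulin, C-peptide and HOMA2.

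**Where the start of medication does matter.** SAP 4.4.1.2 makes starting any diabetes medication a criterion for incident diabetes. SAP 4.5.5.4 states that the hypoglycemia summaries "will exclude hypoglycemic events occurring after initiation of rescue antihyperglycemic medication". Elsewhere such use is only tabulated (SAP 6.1.4).

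**The concern.** An estimand labelled efficacy should attribute Week 72 glycemic status to the randomised treatment. Here a participant whom the SAP itself classes as diabetic, because treatment was started, can later be scored as having returned to normal through that treatment. The credit goes to whichever arm the participant is in.

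The trial has an exploratory objective of delayed progression to T2DM on tirzepatide among participants with IGT at baseline. If that holds, more placebo participants will start these drugs and the placebo improvement rate will be raised more than the tirzepatide rate. Mean glucose and HbA1c would shift in the same direction even without full normalisation.

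The endpoints matter to the trial. Protocol 4.2 stresses improvement of obesity-related health problems as a secondary endpoint, and Protocol 4.1 enriches for IGT. The treatment-regimen estimand in SAP 1.1.2.2 covers body weight only, so no planned supplementary analysis would show the effect of these drugs.

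**Working it through.** **1. The plan's own figure.** Protocol 9.2 and SAP 5 claim more than 90% power for both co-primary endpoints. Inputs: 261 / 3 = 87 per arm, 25% dropout, 87 × 0.75 ≈ 65, two-sided alpha 0.025.
- Weight change (difference 11, SD 10): power above 0.999.
- At least 5% weight loss (25% vs 90%): Fisher's exact power above 0.999.

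The claim reproduces and does not involve glucose. The documents give no power or rates for the IGT or glucose endpoints, so every rate below is an assumption.

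**2. Tracing one participant.** IGT at baseline; diabetes identified at Week 24 or 52 (OGTT visits); a permitted drug started; study drug continued; 0-hour glucose below 110 and 2-hour below 140 mg/dL at Week 72.
- EAS: data kept, because study drug was not stopped.
- IGT improvement: yes.
- Time to T2DM: event.
- MMRM: values after the start of the drug are included.

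Detection at Week 24 leaves 72 − 24 = 48 weeks on medication and detection at Week 52 leaves 72 − 52 = 20 weeks, so the path is feasible. HbA1c at Weeks 12, 36, 48 and 60 can also prompt earlier detection.

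**3. Headcount on placebo.** Protocol 4.1 requires more than 60% with IGT. At that floor, 87 × 0.60 ≈ 52 per arm. Let *c* be the share starting a drug and *f* the share of those who normalise.
- Low: *c* = 3%, *f* = 30%. Inflation 0.03 × 0.30 = 0.9 points; 52 × 0.009 ≈ 0.5 participants.
- High: *c* = 10%, *f* = 50%. Inflation 0.10 × 0.50 = 5 points; 52 × 0.05 = 2.6 participants.

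**4. Loss of risk difference.** If these participants would otherwise be non-improvers, the loss is (*c* placebo − *c* tirzepatide) × *f*, in percentage points:

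| Start rate, placebo vs tirzepatide | *f* = 25% | *f* = 50% | *f* = 100% |
|---|---|---|---|
| equal | 0 | 0 | 0 |
| 2% vs 0% | 0.5 | 1.0 | 2.0 |
| 5% vs 1% | 1.0 | 2.0 | 4.0 |
| 10% vs 1% | 2.25 | 4.5 | 9.0 |
| 15% vs 2% | 3.25 | 6.5 | 13.0 |

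**5. What that could do to the test.** Take 52 × 0.75 = 39 per arm, two-sided alpha 0.05, start rates 10% vs 1% and *f* = 50%. This adds 5 points on placebo and 0.5 on tirzepatide.

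| True improver rates | Counted rates | Odds ratio | Power |
|---|---|---|---|
| 30% vs 80% | 35.0% vs 80.5% | 9.3 to 7.7 | 0.998 to 0.991 |
| 40% vs 70% | 45.0% vs 70.5% | 3.5 to 2.9 | 0.77 to 0.63 |

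With a large true effect almost nothing is lost. With a moderate one the loss is noticeable.

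**The case against.** **Keeping these data is a legitimate strategy.** Retaining values after a permitted concomitant drug amounts to treatment policy for that event. This stands as a possible choice, but the SAP nowhere makes it, and it fits poorly under an estimand labelled efficacy.

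**A reader might infer a demonstrated bias toward the null.** The documents do not support that. They give no start rates, balanced use gives zero attenuation, and the direction depends on more use on placebo. The delayed-progression objective implies that imbalance but does not establish it. If it occurs, the effect is conservative and cannot create a false tirzepatide benefit.

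**The group is small.** Diabetes first found at Week 72 cannot produce a medicated Week 72 improver. Earlier cases may need a repeat test and then depend on an outside provider's decision to prescribe. The participant must also stay on study drug and meet both OGTT cut-offs. This stands.

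**A reader might infer that such a participant automatically succeeds on the composite.** That does not follow. SAP 4.4.1.3 asks for at least two improvements in the lower BMI group, and its responder rule requires at most one remaining problem there and none in the higher BMI group. Normal glucose alone may not suffice.

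**A reader might infer that being both an incident-diabetes event and an IGT improver is a contradiction.** Strictly it is not. One endpoint is first onset in the Safety Analysis Set; the other is Week 72 status in the EAS. The difficulty is what the improvement is credited to.

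**A reader might treat the hypoglycemia exclusion as a precedent for efficacy.** It is a safety rule with its own reason, since glucose-lowering drugs can themselves cause hypoglycemia. It shows only that the start of medication is available to the analysis.

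**Conclusion.** The gap is real and confined to the secondary IGT-improvement and glycemic endpoints and the IGT component of the composite. As written, a Week 72 normalisation produced by another drug counts as IGT improvement, and on-medication values enter the glucose and HbA1c models.

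The size is unknown and probably small. It is about 0.5 to 2.6 of some 52 placebo participants with IGT under the assumed 3-10% starting and 30-50% normalising. Across the wider grid the loss of risk difference runs from zero to 13 points, and the top figure needs 15% vs 2% starting with every starter normalising. These figures rest on the 60% IGT floor, equal arms, and starters being non-improvers otherwise.

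The co-primary weight conclusions are untouched. Strong type 1 error control (SAP 2.1) covers those hypotheses only, so no confirmatory claim depends on this point. It is worth settling before unblinding, because silence leaves the strategy open to choice afterwards.

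**What to change.** In SAP 1.1.2 and 4.4.1.2-4.4.1.3:

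- Name the start of glucose-lowering medication as an intercurrent event for the IGT and glycemic endpoints. Use the start of medication, not incident diabetes alone. Failing everyone who ever met diabetes criteria would also fail a participant who crossed the threshold during the 20-week escalation and normalised on study drug alone, which removes genuine study-drug effect.
- Score participants who start such a drug before the Week 72 assessment as not improved for IGT, and as not improved on the IGT component of the composite.
- For fasting and OGTT glucose, HbA1c, insulin, C-peptide and HOMA2, state the strategy explicitly. Alongside the all-data analysis, add a sensitivity analysis excluding values after the start. Note that it assumes the excluded values are missing at random, which is debatable for participants whose glycemia is deteriorating.

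Cost: SAP wording and one extra analysis, with a few participants reclassified. No new data are needed, since Protocol 6.5 already requires reasons and dates for all medication and Protocol 6.7 records the diabetes diagnosis date in the eCRF. What may be prescribed does not change.
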